#### **6.1.3** Clinical Laboratory Assessments

The following laboratory tests will be performed at Screening Visit 1 and 2, Baseline before first dose of study drug is administered, at Weeks 3-12, Months 6-24, and Month 27 for safety (as indicated below and on the Schedule of Activities; Sec. 7.7):

- o Serum Uric Acid [all visits]
- Complete blood count (CBC) with differential (hematocrit, hemoglobin, platelet count, RBC indices, Total RBC, Total WBC, and WBC & differential) [at baseline and after 3 months and 2 years on treatment; and at all other visits for subjects on potassium citrate alkalinization therapy]
- o Basic blood chemistry panel: bicarbonate, blood urea nitrogen (BUN), chloride, creatinine, glucose, potassium, sodium, GFR [at 2nd screening visit, all on-treatment visits, and safety visit]
- Specialty blood chemistry: Liver function tests (LFTs)/Lipids/ thyroid-stimulating hormone (TSH); LFTs: alanine aminotransferase (ALT (SGPT)), aspartate aminotransferase (AST (SGOT)), albumin, alkaline phosphatase, calcium, magnesium, phosphate, total bilirubin and total protein; Lipids comprise cholesterol, HDL, LDL and triglycerides [at baseline and after 3 months and 2 years on treatment]
- Urinalyses: bilirubin, blood, clarity, color, glucose, ketones, nitrate, pH, protein, specific gravity, urobilinogen and WBC screen; plus urine sediment exam for uric acid crystalluria [at 1st screening visit, all on-treatment visits, and safety visit].
  - O Subjects may be asked to obtain additional urine samples at home if they begin alkalinization therapy (see section 8.4.2 for futher instruction), or they may be given the option to obtain additional urine samples at home as deemed appropriate by the Site Investigator (for example, to ensure subjects are adequately hydrated as assessed by urine specific gravity). If the reason the subject is being asked to collect a urine sample is to monitor their hydration level, study staff should ask subjects to collect this sample anywhere from one week after a visit to one week before the next visit (further guidance can be found in the Manual of Procedures section 13.4). Subjects will be instructed by sites as to how to obtain and send the at-home urine samples to the central lab.
- o 24-Hour urine analysis: chloride, creatinine, pH, potassium, sodium and urate, with total volume [at baseline and 1 year visit]

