#### 8.4 Known Adverse Event / Experience Prophylaxis Plan

## 8.4.1 Monitoring of Urine pH and Uric Acid Crystalluria

Acidic urine is a major, modifiable risk factor for uric acid urolithiasis, which form from uric acid crystals. Thus microscopic uric acid crystals in the urine (uric acid crystalluria; UAC) are an intuitive additional risk factor for these stones. Our experience in SURE-PD provides empiric evidence that identification of uric acid crystalluria by a central laboratory in the setting of low urine pH can in fact provide a useful further indication of increased risk of uric acid urolithiasis. Accordingly, urine samples will be collected at all on-treatment site visits for central laboratory urinalysis to determine pH and the presence of UAC, in a blinded manner. (See Schedule of Activities, Sec. 7.7.) Both risk factors will be

integrated into the following algorithm for triggering urine alkalinization therapy for uric acid stone prophylaxis.

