6.7.6 Alkalinization and Nephrolithiasis

The frequency of persistent acidic urine will be summarized by treatment group and tested by Fisher's exact test in the ST sample. The efficacy of the alkalinization protocol to increase urine pH will be summarized overall in the ST sample. The frequency of nephrolithiasis and the absolute rate of nephrolithiasis per time exposed to study drug will be summarized by treatment group. Risk factors for nephrolithiasis will be tested in a binary generalized linear model with log link and with log time on study drug as an offset. The following risk factors will be tested in a multivariable model:

- age,
- sex,
- treatment,
- uric acid excretion fraction at baseline estimated from serum urate and 24-hr urine urate,
- uric acid crystals/hpf prior to first nephrolithiasis
 - in most recent urinalysis,
 - o average in post-randomization urinalyses,
 - o maximum in any urinalysis,
- urine specific gravity prior to first nephrolithiasis
 - in most recent urinalysis,
 - o average in all urinalyses,
 - o maximum in any urinalysis,
- urine pH prior to first nephrolithiasis

- o in most recent urinalysis,
- average in all urinalyses, and
- o minimum in any urinalysis.

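### SAP 6.7.6 sets no urine window for participants without a stone; on the plainest reading, high maximum specific gravity or crystals and low minimum pH look falsely protective

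*SAP*

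**What the plan says.** SAP 6.7.6 lists three families of urine covariates: "uric acid crystals/hpf prior to first nephrolithiasis", "urine specific gravity prior to first nephrolithiasis" and "urine pH prior to first nephrolithiasis". Each is summarised as the most recent value, the average and an extreme: "maximum in any urinalysis" for crystals and specific gravity, "minimum in any urinalysis" for pH. Risk factors are to be "tested in a binary generalized linear model with log link and with log time on study drug as an offset", within a multivariable model that also contains age, sex, treatment and baseline uric acid excretion fraction.

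No index date, landmark or censoring date is given for a participant without a stone. Only the crystal average is restricted to samples after randomization. The Safety and Tolerability sample (SAP 6.2) does not close the window either, because it keeps observations made after permanent discontinuation of study drug.

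The number of samples grows with follow-up. Protocol 8.4.1 says "urine samples will be collected at all on-treatment site visits for central laboratory urinalysis to determine pH and the presence of UAC". Protocol 6.1.3 lists urinalysis "plus urine sediment exam for uric acid crystalluria" at the first screening visit, all on-treatment visits and the safety visit; Protocol 7.1.8 adds baseline.

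**The concern.** For a case, the window ends at the first stone. For a non-case the phrase has no referent, and the natural programming default is to use every sample on file. The two groups then differ in sample count for a reason unrelated to urine chemistry. A maximum rises, and a minimum falls, with the number of samples behind it. Stone-free participants therefore show higher maximum specific gravity, higher maximum crystal counts and lower minimum pH even when none of these affects stone risk.

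The offset adjusts the event rate for time at risk; it leaves the covariate as computed. What is at stake is the purpose of this model: to show which urine findings predict stones, in a trial where SAP 2.6 records a higher than expected stone rate. An irrelevant marker could be reported as protective, and a real one missed.

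**Working it through.** The documents give no figure for this analysis, so there is none to reproduce.

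**1. Sample counts.** Scheduled urinalyses are SC1, baseline and ten on-treatment visits (12), plus the safety visit (13th). Follow-up is assumed uniform over 9 to 24 months, because SAP 4.8 records early closeout. Under constant stone hazard, cases average 6.2 to 6.3 samples before the stone and non-cases 9.0 (10.0 with the safety visit). If stones occur only after month 4, as in phase 2 (Protocol 2.2.3), the counts are 7.1 to 7.2 against 9.0.

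**2. Why the extreme shifts.** For a Gaussian marker with unit variance and within-person correlation r, the expected maximum of n samples is √(1−r) × E(Mₙ), where E(Mₙ) = ∫ x·n·φ(x)·Φ(x)ⁿ⁻¹ dx. This gives E(M₆) = 1.27 and E(M₉) = 1.49.
- r = 0.4: 0.775 × 1.27 = 0.98 against 0.775 × 1.49 = 1.15.
- r = 0.7: 0.548 × 1.27 = 0.69 against 0.548 × 1.49 = 0.81.

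The gap exists with no effect on stones.

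**3. Stone risk (assumed).** The documents project no rate for this trial. Earlier studies give 25%, 11% and 3.8% (1.2% on placebo) in multiple sclerosis, and 0, 1 and 2 nephrolithiasis events by arm in phase 2. I took 6% (3 of about 50 on inosine in phase 2) to 20% (the threshold in Protocol 10.4.3, which also counts gouty arthritis), with 1.5% on placebo. That yields about 7 to 21 observed stones under constant hazard.

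**4. Simulated size with no true effect.** N = 270 (1:1), r = 0.4 or 0.7, Poisson log-link working model, each summary entered alone, offset ending at the stone. False protection is nominally 2.5%.

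| Gaussian specific-gravity-type summary | Rate ratio per SD | Falsely protective |
|---|---|---|
| Maximum, stones only after month 4 | 0.86–0.95 | 3–10% |
| Maximum, constant hazard | 0.77–0.90 | 4–24% |
| Average or most recent | 0.96–1.07 | about 2–4% |

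A second simulation with follow-up to 24 months, 11 samples for every non-case and correlation 0.3 to 0.6 gave 0.55 to 0.80 and 10 to 59%. It ran the offset both to the stone and over total time; neither removed the bias.

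**5. Other markers.**
- Crystals, set to the phase 2 frequency (7 of about 25 = 28% ever positive): rate ratio 0.77 to 0.85. False protection was 7 to 16% by likelihood-ratio test (3 to 5% with equal windows) but about 0% by Wald test on raw counts.
- Minimum pH, per 0.5 lower: 0.71 to 0.91 and 7 to 26%. This is illustrative only: the simulation omitted the crystalluria-plus-pH alkalinization trigger (Protocol 8.4.2), the changes to the placebo trigger and the January 2018 dosage reduction (SAP 2.6). Average pH is not safe either: when alkalinization was common and strong, it was biased the other way (1.20 to 1.36 per 0.5 lower).

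**6. True effect.** With hazard ratio 1.65 per latent SD and 10 to 20% stone risk, the maximum returned 1.20 to 1.39 with 9 to 29% power. Time-updated Cox returned 1.48 to 1.59 with 27 to 50%.

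**7. Remedy under the null.** Time-updated Cox with the running maximum gave 0.97 to 1.02 and false protection in 1 to 4%. That run stratified by arm, but the mechanism does not depend on stratifying.

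**The case against.** The strongest reply is that SAP 6.7.6 never says one record per participant. A binary log-link model with a log-time offset can be fitted to person-intervals, and the most recent urinalysis before a stone fits that layout well. This stands: the text is under-specified, and the bias is conditional on a reading. It does not dispose of the point, because nothing in the SAP points the programmer to the safe layout, and the average and extreme over all or any urinalyses invite the other one. The dummy-randomization test run in SAP 6.1.4 changes treatment labels, not case and non-case windows, so it would not reveal the problem.

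The size is also open to challenge. It rests on assumed stone risk, timing and correlation, and on a single-summary Poisson fit rather than the multivariable binary model. Phase 2 stones came after more than 4 months, which is the milder scenario. That also stands, so the month-4 figures should be read first.

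A reader might go further and infer that every urine summary is biased, or that the trial's stone findings are unsafe. The documents do not support this. The average and most-recent specific gravity are essentially unbiased, and the stone frequency and rate by arm in the same section use no urine window.

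**Conclusion.** The missing window is a fact of the text. The bias follows only if stone-free participants contribute every sample, which is the plainest reading but not a stated one. On that reading the direction is clear: maximum specific gravity, maximum crystals and minimum pH are pushed towards apparent protection, and a true effect is attenuated. For a specific-gravity-type maximum the size is modest if stones come late and larger under constant hazard. With so few stones, power is low under any layout. How often crystals reach significance depends on the test, and no firm size can be given for pH. It would be too strong to say that the planned analysis is shown to be biased, or that a harmful marker will always appear protective; a strong effect is weakened rather than reversed. This is an exploratory safety model with no decision rule attached.

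**What to change.** In SAP 6.7.6, define the same urine window for cases and non-cases. Preferably use time-updated covariates, either by keeping the binary log-link model on person-intervals or by Cox regression. At each risk time, compute the latest value, running mean and running maximum (minimum for pH) only from urinalyses before that time, for everyone still at risk. A person-interval model should include a time term, because running extremes grow with time. Alternatively, give non-cases risk-set-matched index dates and cut their window there.

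State that time on study drug ends at the first stone for this model (Protocol 8.5.1 allows dosing to resume afterwards), and whether safety-visit and home samples count. Keep treatment as a listed risk factor. Entering the three summaries of an assay in separate models is optional.

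The cost is a few lines of text and modest extra programming on data already collected; SAP 6.7.5 already plans a Cox model with a time-dependent covariate.

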6.8 Other Analyses

6.8.1 Participant Disposition

The number of participants who were screened, randomized, completed scheduled follow up, and prematurely withdrew study participation will be summarized overall and by treatment group. Reasons for screen failure and for withdrawal from study will be presented.

6.8.2 Study Drug Exposure

The number of capsules of study drug prescribed will be summarized by visit and treatment group. Total study drug exposure will be calculated and will be summarized by treatment group. Compliance with study drug will be calculated as the number of doses taken divided by the scheduled number of doses taken prior to permanent discontinuation, expressed as a percentage.

6.8.3 Prior and Concomitant Medication Use

Concomitant medications taken during the study period will be listed for each participant, coded using the World Health Organization Drug Dictionary Enhanced. The percentage of participants taking each class of medication will be summarized overall and by treatment group.

6.8.4 Determinants of change in MDS-UPDRS

Potential determinants of change in MDS-UPDRS will be tested to assess their relationship to PD progression independent of serum urate elevation. This may motivate further adjustment of the primary model as additional secondary analyses and may also assist in the design of future trial. In addition to those noted above in 6.6.1, we will test the following:

- Prodromal PD features, either individually or as an index
 - Positive RBD screen at SC1 or BL
 - RBD characterization: At SC1, do those who are RBD-positive vs negative (2 vs. 1 on Q1 of RBD Sleep Question) have higher age- and sexadjusted serum urate?
 - Positive hyposmia screen: Response of 1 on Q9a of the PD Risk Factor Questionnaire
 - Hyposmia characterization: Do hyposmics (1 on Q9a vs. 0 on Q9) have lower age- and sex- adjusted BMI at SC2?
 - Positive constipation screen: Response of >2 on Q1.11 of MDS-UPDRS at SC2 or daily (non-prn) laxative use on concomitant medication log at SC2
 - Constipation characterization: Do those who are positive by this moderately stringent criterion have a:
 - Lower current, vigorous physical activity score (Q3 on PD Risk Factor Questionnaire; among those selecting response 1-4)?

- Lower caffeine intake (Q3-4 on Smoking, Alcohol and Caffeine Status)
- SURE-PD3 prodromal PD Index (range 0, 1, 2 or 3) with simple sum values for presence (= 1) for each of above three features.

6.8.5 Determinants of Early Disability Warranting Dopaminergic Therapy

An earlier, mid-study effort to identify determinants of need for dopaminergic therapy occurring prematurely (by the 12-week visit) was prompted by a higher than expected rate of these events and a concern that it would reduce study power to meet its primary analysis objective. Modified Schwab and England ADL score at screening was identified as a significant predictor, and site staff were advised to keep in mind that a Modified Schwab and England ADL score below 90% was predictive of premature need for dopaminergic therapy, the expectation of which is an exclusionary criterion. Because this clinical eligibility criterion is common in PD trials of candidate neuroprotectants, a fuller assessment of predictors would be valuable.

The following potential determinants of Early Disability Warranting Dopaminergic Therapy will be tested: Modified Schwab and England ADL score, time between symptom onset or diagnosis and baseline visit, having taken dopaminergic medication (other than an MAO-B inhibitor) prior to screening, being on a stable dosage of an MAO-B inhibitor at baseline, baseline MDS-UPDRS Part I-III total score, DaTscanTM SBR, expectation of improvement on inosine (on Expectancy Questionnaire), baseline Neuro-QOL Depression score, and baseline MoCA score.

6.8.6 Placebo Response

The frequency of a placebo-associated improvement in activities of daily living (ADL) and motor symptoms as measured by the MDS-UPDRS Parts IB and II and Part III, respectively, will be summarized among all placebo arm participants, by visit, and by site. Following Goetz et al. 2000, we will define placebo-associated improvement as a reduction in the ADL or motor score of at least 50% or an improvement from baseline of two or more points on at least two different items of the respective MDS-UPDRS scale. Stability of the rates of placebo-associated improvements will be tested across visits using mixed model logistic regression with fixed effects of visit and random participant-specific intercepts. The following predictors of placebo-associated improvement at any visit will be tested by logistic regression:

- age at baseline (less than 65 years versus greater or equal to 65 years),
- disease duration at baseline (less than 2 years vs. greater or equal to 2 years),
- disease severity at baseline (modified Hoehn and Yahr Stages 1 and 1.5 vs. 2 and 2.5),
- number of years education (Q1 on Socio-Economics form)
- daily caffeine intake: lower vs higher (Q3 + 0.3xQ4 from Smoking, Alcohol and Caffeine form)
- expectation of inosine: "A lot better" vs "Somewhat better" vs "No change" or worse (Q2 on PD-Expectancy questionnaire)
- expectation of inosine-placebo difference: >/=2 vs <2 units more favorable for inosine (Q2 - Q1 on PD-Expectancy questionnaire)
- preference for inosine: "strong" vs other (Q3 on PD-Expectancy questionnaire)
- treatment belief: placebo vs inosine (Q2 on Blindedness Questionnaire).

6.8.7 Blindedness

Descriptive stats will be summarized for responses on the early and late administrations of the Blindedness Questionnaire and the change between them. The following predictors of treatment assignment belief reported on the Blindedness Questionnaire will be tested by logistic regression. For belief of inosine assignment (stratified by correct and incorrect):

- age at baseline (categorized as <65 years vs. ≥ 65 years)
- sex
- treatment assignment
- MDS-UPDRS I-III censored change at wash-in (per 6.6.8) for response at the 6-week (V02) administration
- MDS-UPDRS I-III censored change to \sim 24-mo/V10 for response at the \sim 24-mo/V10 administration
- history of preceding nephro-lithiasis TEAE
- history of preceding gout, gout-like or other arthritic TEAE
- average preceding daily number study drug capsules
- expectation of inosine: "A lot better" vs "Somewhat better" vs "No change" or worse (Q2 on PD-Expectancy questionnaire),
- expectation of inosine-placebo difference: >/=2 vs <2 units more favorable for inosine (Q2 - Q1 on PD-Expectancy questionnaire)
- preference for inosine: "strong" vs other (Q3 on PD-Expectancy questionnaire).

7. References

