4.7 Blinding

The presumed treatment group to which a participant was assigned, a respondent's confidence in that presumption, and the reason for that presumption will be collected from participants, site investigators, and coordinators at the 6 week visit and at the end of treatment. The proportion guessing correctly or incorrectly and the odds ratio of guessing the true treatment vs. the wrong treatment will be evaluated for each class of respondent, both overall and among the subset of respondents who assert being at least somewhat sure of their guess.

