6.6.8 Symptomatic Effects

The presence of symptomatic effects will be tested using a change-point model constructed as a partial linear spline over time with knots at 12 weeks and 24 months. Both fixed and subject-specific random terms for intercept, slope from baseline to 12 weeks, slope from 12 weeks to 24 months, and slope from 24 to 27 months (or from V10-equivalent visit on study drug to SV) will be included. Unstructured covariance will be assumed among the random effects (10 terms). The AT sample will be analyzed. Significantly smaller slopes during wash-out among subjects treated with inosine using one-sided testing at alpha = 0.025 will be interpreted as symptomatic effects. If symptomatic effects are not found on that basis, the absence of symptomatic effects will be judged based on a non-inferiority test using a non-inferiority bound of 6.3 / 3 = 2.1 points/month in the direction of a symptomatic effect and using one-sided testing at alpha = 0.05.

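### SAP 6.8.7 lists treatment assignment as a predictor of belief within strata in which it cannot be estimated, and predicts the week-6 answer partly from later scores

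*SAP*

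**What the plan says.** SAP 6.8.7 states the method: "The following predictors of treatment assignment belief reported on the Blindedness Questionnaire will be tested by logistic regression". The models are set up "For belief of inosine assignment (stratified by correct and incorrect"), followed by eleven predictors. One is "treatment assignment" itself. Five are baseline factors: age, sex and three items from the expectancy questionnaire. The other five arise after randomisation: two MDS-UPDRS changes, "history of preceding nephro-lithiasis TEAE", gout-like or arthritic events, and "average preceding daily number study drug capsules".

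SAP 4.7 shows what correct and incorrect mean, since it plans "The proportion guessing correctly or incorrectly and the odds ratio of guessing the true treatment vs. the wrong treatment". SAP 2.5 gives two arms in equal proportions.

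For the early questionnaire, the MDS-UPDRS predictor is "MDS-UPDRS I-III censored change at wash-in (per 6.6.8) for response at the 6-week (V02) administration". SAP 6.6.8 defines the wash-in segment as the "slope from baseline to 12 weeks", and SAP 3.5 likewise describes wash-in as the first 3 months.

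**The concern.** With two arms, knowing what someone believes and whether they were right tells you their arm. Stratifying on correctness while modelling belief therefore fixes the relation between outcome and arm inside each stratum, and arm is also on the predictor list.

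The analysis is meant to show what led people to their guess. That question matters in this trial because the primary outcome combines patient-reported and investigator-rated parts (SAP 5.1). Protocol 3.2.4.2 treats stones as a possible route to unblinding, phase 2 recorded 0, 1 and 2 stones in the placebo, mild and moderate groups (Protocol 2.2.3), and SAP 2.6 reports more stones than expected. If the model turns an arm difference in stones into an apparent effect on belief, it cannot show whether stones revealed treatment.

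The timing point is separate. A predictor of an answer given at week 6 should not contain scores recorded afterwards.

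**Working it through.** The plan gives no figure for this analysis, so there is none to reproduce.

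**1. Identity.** Let A = 1 for inosine and B = 1 for believing inosine. A guess is correct when B = A.
- Correct stratum: B = A for everyone.
- Incorrect stratum: B = 1 − A for everyone.

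In a simulated trial of 270, belief equalled arm for all 152 correct guessers and its reverse for all 118 incorrect guessers. Adding assignment to the correct-stratum model gave complete separation (coefficient about 62, with no finite maximum).

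**2. What the other coefficients estimate.** Let f₁ and f₀ be the distributions of a predictor X in the inosine and placebo arms, and p₁(X) and p₀(X) the probabilities of believing inosine. By Bayes, up to a constant, the log-odds of B = 1 are:
- correct stratum: log[f₁(X)/f₀(X)] + log[p₁(X)/(1 − p₀(X))]
- incorrect stratum: −log[f₁(X)/f₀(X)] + log[p₀(X)/(1 − p₁(X))]

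The first term is the arm difference in X, with opposite signs in the two strata. It vanishes when X has the same distribution in both arms.

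**3. Stones, with random guessing.** The second terms are then constant. The stone rates are assumptions, because the documents give none for this trial by arm.

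| Assumed stones, inosine vs placebo | OR, correct stratum | OR, incorrect stratum | OR given arm |
|---|---|---|---|
| 5% vs 2% | (0.05/0.95)/(0.02/0.98) = 2.58 | 1/2.58 = 0.39 | 1 |
| 10% vs 2% | (0.10/0.90)/(0.02/0.98) = 5.44 | 1/5.44 = 0.18 | 1 |

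A simulation of one million subjects at 10% vs 2% gave 5.36 and 0.18. When stones truly affected belief (OR 2.72, with an arm effect on belief as well), the strata returned 13.2 and 0.57. One model in all respondents with arm included returned 2.76; models within arm returned 2.76 and 2.75.

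**4. Chance of a false signal at this trial's size.** With 135 per arm and random guessing, the stone term in the correct stratum reached p < 0.05 by likelihood-ratio test in about 57% of simulated trials at 10% vs 2%, and in about one in five at 5% vs 2%. By Fisher's exact test the figures were about 42% and 7%.

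**5. Balanced baseline predictors.** For a baseline factor with a true OR of 2.01, the strata gave 2.02 and 2.01 without an arm effect on belief, and 1.87 and 2.20 with one.

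**6. The other reading.** If the strata mean inosine-arm and placebo-arm participants, each model is fitted within one arm. The other terms are then valid and the ratios in step 3 do not arise, but assignment takes a single value in each model and drops out.

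**7. Timing.** The first blindedness questionnaire is at V02 (day 42 ± 5). The 6.6.8 wash-in segment ends at 12 weeks, which is V03 (day 84 ± 7). MDS-UPDRS Parts I-III are collected at V02 (SAP 2.8; Protocol 7.2.3), so a change ending at the right visit is available.

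**The case against.** The wording may simply mean correct belief in inosine (inosine arm) and incorrect belief in inosine (placebo arm), which is modelling by arm and sound. On that reading the defect is one redundant row. This is a fair reading, but the SAP does not state it, SAP 4.7 uses correct and incorrect for the guess against the true treatment, and listing assignment does not fit it.

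A reader might infer that every listed predictor collapses into a comparison of the arms. That is too strong: the five baseline factors are balanced by randomisation and are estimated about right (step 5). A reader might also infer that a strong false stone signal is certain. It is not: the size depends on stone rates that the documents do not give by arm, and step 4 shows that it could often go undetected. Phase 2 stones came only after more than 4 months on drug (Protocol 2.2.3), so the stone problem mainly concerns the late questionnaire. Capsule count is a weak example, since placebo titration is designed to match active counts (Protocol 5.1.2.3; SAP 2.7); it is distorted only if that matching is imperfect.

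The question of what revealed treatment does not rest on 6.8.7 alone. Respondents also give reasons for their guess (SAP 4.7 and 5.15), although the SAP sets out no analysis of those reasons beyond descriptive summaries. The test tables under a dummy randomisation (SAP 6.1.4) should expose the failure of the assignment term, but not the distortion in the other rows.

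**Conclusion.** The point holds as a defect in a secondary blinding analysis. Treatment assignment cannot be estimated under either reading of the strata, and nothing else in the documents resolves which reading is meant.

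If the strata are correct and incorrect guessers, predictors that differ by arm (stones, gout-like events, MDS-UPDRS change, and capsule count if matching is imperfect) mix the arm difference into the belief effect with opposite sign in the two strata. For stones this gives odds ratios of about 2.6 to 5.4 and 0.39 to 0.18 where the value given arm is 1, assuming random guessing and rates of 5% to 10% on inosine against 2% on placebo. If the strata are the arms, only the assignment term fails.

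The week-6 timing defect holds under both readings.

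It would be wrong to conclude that the blinding assessment as a whole, or the trial's main result, is compromised. The proportions and odds ratio in SAP 4.7 do not use these strata, and no primary efficacy, safety or stopping decision draws on 6.8.7.

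**What to change.** In SAP 6.8.7:
- Drop stratification by correctness.
- Either model belief (inosine vs placebo) in all respondents, with assignment, the listed predictors and predictor-by-assignment terms, or fit separate models by randomised arm and remove assignment from the list. With few stones or gout-like events the interaction terms will be imprecise, so report confidence intervals.
- For the week-6 answer, replace the wash-in change per 6.6.8 with the MDS-UPDRS I-III change from baseline to V02, keeping the same censoring at initiation of dopaminergic therapy.

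The cost is a few lines of SAP wording and a small programming change before unblinding. No new data are needed.
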